9.4. Dealing with dropped out, excluded patients and missing data

No missing data will be completed, missing data will not be taken into account when performing statistical analyses.

9.5. Outliers

Identification of questionable data and data that cannot be analysed can be done by visual analysis of scatter plots, boxplots, etc. Statistical analyses will be performed on outlier data and then on the outlier-cleaned sample.

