9. STATISTICS

9.1. Calculation of sample size

The sample size calculation was based on the results of the Phase III clinical trial of Mexidol® [Multicentre randomized double-blind placebo-controlled parallel-group trial of the efficacy and safety of MEXIDOL® (solution for intravenous and intravenous administration / coated tablets) in long-term sequential therapy in patients with hemispheric ischaemic stroke in

the acute and early recovery periods - (EPICA)] dated 30.09.2016.

The trial plans to test the hypothesis of "superiority" of therapy with the investigational product vs. placebo therapy. The following indicator was chosen as the primary efficacy criterion: "The magnitude of change in the patient's **mRS** (Modified Rankin Scale) score at the end of therapy (Day 71) vs. baseline (in points)"

In the case of a superiority trial, the null hypothesis (H_0) and the alternative hypothesis (H_1) are formulated as follows:

$$H_0: \varepsilon = \mu_T - \mu_p \leq \delta, H_1: \varepsilon > \delta, \delta > 0, \text{ where}$$

- ε is the true difference between the value of the primary efficacy index (μ_T) in the group of patients taking the investigational product (T) and the value of the primary efficacy index (μ_p) in the group of patients taking placebo,
- δ - the boundary of "superiority" of therapy with the investigational product compared to placebo therapy by the primary efficacy indicator.

To prove superiority of therapy with an investigational product compared with placebo therapy, the lower bound of the 95% one-sided confidence interval (CI) for the difference in values of the primary efficacy criterion ($\mu_T - \mu_p$) must be greater than δ , where $\delta > 0$, i.e. CI must fall within the interval $(\delta, +\infty)$.

To calculate the sample size, data from the EPICA clinical trial were used for the ITT population (patients who received the investigational product or placebo at least once), as this population allows us to draw conclusions about the efficacy of the investigational therapy on the population closest to the patient population in real clinical practice. The results of the previously conducted EPICA clinical trial are summarized in Table 9.1.

Table 9.1. *Change in mRS score at the end of therapy relative to baseline [Visit 1 (Day 1) to Visit 5 (Day 67-71)] in patients enrolled in the ITT population.*

[μ - arithmetic mean; SD - standard deviation, DM - difference in mean averages]

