Patient group	Group	$\mu \pm SD$	Efficacy evaluation:	
			95% CI for the difference in mean ($\mu_{\text{Mex.}} - \mu_p$)	Comparison between groups
ITT population (n = 144)	Group I (Mexidol®, n = 72)	2.278 ± 0.755	DM = 0.292 (0.027; 0.556)	p = 0.029 (Mann-Whitney U-test)
	Group II (Placebo, n = 72)	1.986 ± 0.847		

According to the results of the EPICA clinical trial, the mean value of the change in the mRS score at the end of the course of therapy relative to the baseline level in the group of therapy with the investigational product was (mean (SD)) 2.278 (0.755) points, in the placebo group - 1.986 (0.847) points 2.278 (0.755) points, in the group of placebo therapy - 1.986 (0.847) points, the difference (Mexidol® - placebo) is 0.292 points, 95% confidence interval for the difference (Mexidol® - placebo) is (0.027, 0.556). The "superiority" boundary (δ) was chosen as the lower boundary of the confidence interval constructed for the difference (Mexidol® - placebo). Thus, $\delta = 0.027$ points.

To test the hypothesis of "superiority" of therapy with the investigational product compared with placebo therapy **at a significance level of $\alpha = 0.05$ (5%) to ensure power $1-\beta = 0.8$ (80%)**, the sample size was calculated for the primary efficacy criterion given the parallel design, a 1:1 randomization scheme (i.e., $k = 1$ - the ratio of sample sizes of the groups n_T/n_p), the expected difference in efficacy between the compared products $\varepsilon = 0.292$ and with a mixed standard deviation (SD) of the in-group efficacy $\sigma = 0.802$ points.

The formula [Chow Sh.-Ch., Shao J., Wang H., 2008] was used in the calculation:

$$n_T = n_R \frac{\frac{(1 + 1/k) * (z_\alpha + z_\beta)^2 * \sigma^2}{(\varepsilon - \delta)^2}}{\frac{2 * (1.6449 + 0.8416)^2 * 0.802^2}{(0.292 - 0.027)^2}} \approx 114 \text{ people/gr,}$$

where z_α and z_β - quantiles of the normal distribution $N(0,1)$ (mean: 0, standard deviation: 1).

The minimum number of patients completing the trial in accordance with the protocol must be at least $N = 2 * 114 = 228$ patients (114 patients per group).

Given the possible attrition of patients in the trial, it is planned to **randomize 304 patients**, of whom **at least 228 should complete the trial according to the Protocol**.

Given the potential dropout of patients during the Screening phase, approval is planned for a clinical trial with a total of **336 screened patients**.

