9.8. Significance level and power of the criterion

The level of significance (genus I error α) was chosen to be 0.05 (5%) and the power of the criterion was chosen to be at least 0.8 (80%).

Since an interim data analysis is planned, a genus I error correction approach α ($\alpha = 0.0294$)¹ will be used to prove the hypothesis of "superiority" of investigational product therapy over placebo therapy on the primary efficacy criterion.

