APPENDIX 2.

mRS (Modified Rankin Scale)

Example form

Tick only one box

- Complete absence of symptoms (0 points)
- No significant disability despite the presence of symptoms: the patient can perform all his/her daily duties and activities (1 point)
- Mild incapacity: the patient is unable to perform his/her usual work, but is capable of self-care without assistance (2 points)
- Moderate disability: sometimes requires assistance but can walk independently (3 points)
- Moderately severe disability: the patient cannot walk unaided and is unable to perform self-care without assistance (4 points)
- Severe disability: patient is bedridden, incontinent of urine and faeces, needs constant care (5 points)
- Death (6 points)

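### Protocol 9.5 repeats the analyses after removing outliers picked by eye, and neither document says whether the full or the cleaned result decides superiority.

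*Protocol*

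**What the plan says.** Protocol 9.5 is two sentences long. Identifying suspect values "can be done by visual analysis of scatter plots, boxplots, etc". Then: "Statistical analyses will be performed on outlier data and then on the outlier-cleaned sample". It gives no cut-off, does not say who decides or whether that person is blind to treatment, and does not confine removal to recording errors. It also does not say what follows if the two results disagree.

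The success rule, in protocol 9.1 and SAP section 7, is that "the lower bound of the 95% one-sided confidence interval (CI) for the difference in values of the primary efficacy criterion" must exceed the margin of 0.027 points.

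The rest of the plan does not settle which result counts:
- The SAP has no outlier rule. Its section 3 plans no departures from the protocol, so 9.5 stands.
- SAP section 9 makes all data subject to analysis, but 9.5 also analyses all data before cleaning.
- Protocol 9.10 and SAP section 9 plan a sensitivity analysis for data errors that cannot be resolved. Valid extreme scores are not covered.
- SAP Table 4 has one row for the primary result and does not say which dataset fills it.

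**The concern.** The mRS is an integer scale from 0 to 6 with entry at 3 or more, so every integer change that is possible from a patient's baseline may be that patient's true outcome. A boxplot cannot tell a recording error from a real result. Removing valid scores changes the group means and shrinks the variance that the confidence interval rests on.

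Two primary results will therefore exist, and nothing in the plan ranks them. If the cleaned result may support the claim, the 5% error rate in protocol 9.8 is no longer assured, and the answer depends on a fence that nobody has specified.

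**Working it through.** **1. The plan's own figure.** Inputs from protocol 9.1: expected difference 0.292, margin 0.027, SD 0.802, one-sided 5%, power 80%.

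n per group = 2 x (1.6449 + 0.8416)² x 0.802² / (0.292 - 0.027)² = 113.26, so 114. This reproduces, with power 80.2% at 114.

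**2. How close a reversal can be.** SE = 0.802 x √(2/114) = 0.1062. The observed difference must exceed 0.027 + 1.6449 x 0.1062 = 0.202.

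Suppose 0.18 is observed (placebo mean change 1.986, active 2.166). The lower bound is 0.18 - 0.175 = 0.005, which fails. Now remove one active-arm patient with a change of -1:
- active mean = (114 x 2.166 + 1)/113 = 2.194, so the difference is 0.208;
- active variance falls from 0.643 to 0.559;
- lower bound = 0.208 - 1.6449 x √(0.559/113 + 0.643/114) = 0.039, which passes.

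The same calculation for other near-misses:

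| Observed difference | Active-arm patients removed to reverse a failure |
|---|---|
| 0.195 | 1 (change 0, -1 or -2) |
| 0.18 | 1 (change -1 or -2) or 2 (change 0) |
| 0.15 | 2 (change -1 or -2) or 3 (change 0) |

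This shows fragility only, because it removes low values from one arm.

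**3. Simulation of a fixed cleaning rule.** These assumptions are mine, not the plan's: 114 per arm, no deaths, normal changes rounded to integers, and a 1.5 x IQR fence. Means are 1.986 on placebo and 1.986 plus the true difference on active. SDs are either a common value of about 0.80 or the EPICA arm values of 0.755 and 0.847. Success means a one-sided 95% lower bound above 0.027. Runs used 4,000 to 8,000 trials.

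| True difference | All data | Fence per arm | One pooled fence |
|---|---|---|---|
| 0.027 (margin) | 4.9-5.5% | 13.7-15.1% | 5.0% |
| 0 | 3.2% | 11.2% | not run |
| 0.292 (planned) | 75-76% | 77.5% | 63-68% |

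Full-data success is about 75% and not 80% because rounding adds about 1/12 to the variance: √(0.643 + 0.083) = 0.852. The pooled result is 63% with the EPICA arm SDs and 68% with a common SD of 0.802.

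**4. How often the two conclusions differ at the planned effect.** With per-arm fences and the EPICA SDs it is 8.7% of trials (5.5% gained by cleaning, 3.2% lost). With a common SD it is about 10-11%. With a pooled fence and the EPICA SDs, success falls from 75.6% to 62.9%, so at least 12.7% must differ.

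**5. Who is removed under per-arm fences.** At the planned effect, about 2.0 of 4.9 removed values per trial are patients with no improvement. At the margin it is 2.3 of 11.7. The rest are patients who improved.

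**The case against.** **The order in 9.5 implies that the full data lead.** The full analysis comes first, 9.10 sends questionable data to query, and Table 4 has a single primary row. This is a reasonable reading, and querying errors is indeed already planned. But it remains an inference: no sentence gives the full analysis precedence, and the query process does not address valid extreme scores.

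**The direction of bias comes from the assumed fence.** This stands. Per-arm fences inflate false success, while a pooled fence does not and costs the drug power. So it cannot be said that cleaning favours the drug. The fair claim is that an unspecified rule can move the result either way.

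**A reader might infer that cleaning would strip out deaths and hide harm.** The mRS form does include "Death (6 points"), but the documents do not support this for the primary analysis:
- Superiority is decided in per-protocol completers (protocol 9.6 and 9.7.2) and missing data are not imputed (9.4), so patients who die would normally be absent.
- Deaths could enter only the additional ITT analysis, and only if scored 6. No analysis section says that they are.
- No death rate is given for this trial. EPICA reported no deaths, with 150 patients in its safety analysis (protocol 2.3.2). The one-sided 95% upper limit is 1 - 0.05^(1/150), about 2%. EPICA admitted a different NIHSS range (5-20 against 9-15 here), so the rate may differ.

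A scenario such as 8% deaths on drug against 5% on placebo, at 152 per arm, is thus a hypothetical ITT illustration and says nothing about the planned primary result.

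**A reader might also infer that flagged values are the bad outcomes.** Step 5 shows that under per-arm fences most are patients who improved.

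**Conclusion.** The concern holds in limited form. Protocol 9.5 orders a second analysis on data cleaned by eye, and neither document says which result decides superiority. At the planned per-protocol size with no deaths, letting the cleaned result decide gives a false-success rate of about 5% or 14-15%, and success at the planned effect anywhere from about 63% to 78%, depending only on how the fence is set and which SDs are assumed. Full and cleaned conclusions differ in about 9-11% of trials at the planned effect, and in at least 12.7% under one setting.

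These sizes rest on rounded-normal changes and a 1.5 x IQR rule, neither of which is in the plan. The missing precedence rule rests on the text alone. The documents do not support a claim that the primary analysis would discard deaths, or that cleaning has a fixed direction of bias.

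**What to change.** State in protocol 9.5, and repeat in the SAP:
- The analysis of all observed data alone decides superiority.
- Values are corrected or excluded only for documented data errors, resolved by query before unblinding.
- Valid mRS, NIHSS, MoCA, HADS and Rivermead scores are not removed as outliers.
- Any analysis of a cleaned sample is a labelled sensitivity analysis.

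This takes a few sentences in each document. The sample size stays at 114 per group (228 completing, 304 randomized). The only cost is that the cleaned result can no longer support the superiority claim.

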9.6. Population to be analysed

The following population groups will be used for the analyses:

1. The ITT (Intent-to-treat) population will include all randomized patients regardless of investigational product/placebo administration.
2. The mITT (modified Intent-to-treat) population will include patients who have completed the full course of therapy, regardless of the presence of Protocol violations/ deviations.
3. The PP (Per protocol) population will include patients who completed the trial in accordance with the Protocol.

At the stage of statistical data processing, additional analyses of the efficacy and/or safety of investigational product/placebo in subpopulations of patients of different age groups can be performed.

9.7. Statistical methods

The choice of statistical analysis method will be determined by the type of raw data and the type of distribution. The feasibility of using a range of statistical techniques will be assessed after data collection is completed, as the nature of the data distribution, sample homogeneity, etc. is not known in advance.

During the course of the analysis, it is possible to expand the list of methods used if this is necessary for the qualitative treatment of the data.

9.7.1. Assessment of demographics and data at the start of the trial

A summary of the group distribution of patients randomized into the trial will be presented. Comparative analyses will be performed to demonstrate comparability of treatment groups on demographic and other baseline patient characteristics.

Categorical (qualitative) data will be described using frequencies, percentages or fractions. Comparison of the frequencies of indicators between patient groups (I and II) will be performed using Pearson's χ^2 test if the frequency in each cell is ≥ 5 , otherwise using Fisher's exact criterion.

Interval (quantitative) data will be described using: arithmetic mean, standard deviation, median, minimum, maximum, lower (25%) and upper (75%) quartiles, coefficient of variation. Comparison of indicator values between groups I and II will be performed using the non-parametric Mann-Whitney U-test for two independent samples distributed according to a non-normal distribution law, or using the parametric Student's t-test for two independent samples if the data in each group follow a normal distribution law.

The Shapiro-Wilk criterion will be checked for conformity to the normal distribution law.

9.7.2. Statistical methods for assessing efficacy

The primary population for the evaluation of efficacy criteria, proof of the hypothesis of superiority of the trial drug therapy over placebo based on the primary efficacy criterion score,

will be the PP population.

Additionally, efficacy criteria will be analysed in the ITT and mITT populations.

This approach in selecting the population for analysis is based on the design of the planned clinical trial: patients in both the investigational product and placebo groups will receive standard (baseline) therapy (according to the Clinical Guidelines "Ischaemic Stroke and Transient Ischaemic Attack in Adults", 2015) with proven efficacy. Therefore, the use of the ITT population for a more conservative assessment of ongoing therapy is inappropriate, as this approach markedly offsets the clinical effects of the investigational product. Therefore, to compensate for the therapeutic effects of baseline therapy and to properly evaluate the effects of IP, the PP population is considered as the primary population for analysing efficacy parameters in the planned trial.

The trial plans to test the hypothesis of "superiority" of therapy with the investigational product vs. placebo therapy. The following indicator was chosen as the primary efficacy criterion: "The magnitude of change in the patient's **mRS** (Modified Rankin Scale) score at the end of therapy (Day 71) relative to baseline (in points)".

In the case of a superiority trial, the null hypothesis (H_0) and the alternative hypothesis (H_1) are formulated as follows:

$$H_0: \varepsilon = \mu_T - \mu_p \leq \delta, \quad H_1: \varepsilon > \delta, \quad \delta > 0, \text{ where}$$

- ε is the true difference between the value of the primary efficacy index (μ_T) in the group of patients taking the investigational product (T) and the value of the primary efficacy index (μ_p) in the group of patients taking placebo,
- δ - the boundary of "superiority" of therapy with the investigational product compared to placebo therapy by the primary efficacy indicator.

To prove superiority of therapy with the investigational product compared to placebo therapy, the lower bound of the 95% (or 97.06% in the case of a phase II trial) one-sided confidence interval (CI) for the difference in values of the primary efficacy criterion ($\mu_T - \mu_p$) must be greater than δ , where $\delta > 0$, i.e. CI must fall within the interval $(\delta, +\infty)$.

Interval (quantitative) data will be described using: arithmetic mean, standard deviation, median, lower (25%) and upper (75%) quartiles, minimum, maximum and coefficient of variation. Categorical (qualitative) data will be described using frequencies, percentages and/or fractions.

To compare quantitative data distributed according to the normal distribution law, it is planned to use standard parametric criteria: Student's t-test for dependent/independent samples, analysis of variance (ANOVA) for repeated measures.

It is planned to use standard nonparametric criteria to compare quantitative data distributed according to a law other than normal: Mann-Whitney U-test, Wilcoxon T-test, Friedman's criterion.

The test for conformity to the normal law of distribution will be carried out using the Shapiro-Wilk test.

Comparisons of frequencies of indicators between treatment groups will be made using Pearson's χ^2 test or Fisher's exact test.

9.7.3. Statistical methods for assessing the safety of using the investigational product and the comparator product

Safety parameters will be analysed in the ITT population.

Safety data will be analysed using the methods outlined for the application of the efficacy data assessment. Analyses of AEs will be performed based on an assessment of the incidence of adverse events / serious adverse events. Adverse events reported during the course of the trial will be presented by frequency (number of patients with AEs and number of such AEs in the group). AEs will also be presented by severity and relationship to investigational product

administration. Comparison of the number of patients with AE between therapy groups will be performed using Fisher's exact test or Pearson's χ^2 test.

